7.3 Variables

Variables to be considered in this analysis as baseline, exposure, treatment, and outcome variables are described in Table 3 (demographic and clinical variables), Table 4 (lenalidomide therapy and other treatment variables), and Table 5 (outcome variables for safety).

The following data variables will be collected from the registries according to local medical practice and availability of data.

Table 3:Demographics and Clinical Variables for Both On- and Off-label
Cohorts

Variables ^a	
Demographics	
Age	Age
Sex	Male/female
Country	Country
Clinical Variables (Baseline Ch	aracteristics)
Date of MDS Diagnosis	Date of initial MDS diagnosis
Date of First Dose of Lenalidomide	Date of first record of lenalidomide treatment initiation
Cytogenetic Abnormalities ^b	Karyotype information, method of diagnosis
Prior invasive malignancy	Yes/No and date/type of previous malignancy, previous therapy (yes/no/unknown for surgery, radiation, chemotherapy)
Bone Marrow and Peripheral Blood Morphology	Bone marrow blast count (%) – at baseline and until disease progression; other bone marrow findings according to the WHO classification: dysplasia by lineage, ringed sideroblasts/erythroid precursors, and Auer rods at baseline
Transfusion Burden	Transfusion burden (units/8 weeks); before lenalidomide treatment initiation and until PD or last follow-up date
Hemoglobin Level	Hemoglobin level; at baseline and every 6 months until PD or last follow-up date
Ferritin level	Ferritin level; at baseline
Platelet Count	Platelet count; at baseline and every 6 months until PD or last follow-up date
Neutrophil Count	Neutrophil count; at baseline and every 6 months until PD or last follow-up date
Endogenous EPO Level	EPO level; at baseline
Risk Classification	Classification as per IPSS

Variables ^a		
Relevant Medical History	Prior history of cardiovascular events (eg, angina/coronary artery disease, MI, CHF, arrhythmia, hypertension, peripheral arterial disease, cerebrovascular event); thromboembolic events (VTEs); pulmonary, hepatic, pancreatic or renal disease; diabetes; prior invasive malignancy, prior NMSC; past life-threatening illness in other organ system.	
Comorbidities	Current cardiovascular or cerebrovascular disease, chronic VTE, current pulmonary, hepatic, pancreatic or renal disease, diabetes, current life-threatening illness in other organ system	

Table 3: Demographics and Clinical Variables for Both On- and Off-label Cohorts

CHF = congestive heart failure; EPO = erythropoietin; EU = European Union; IPSS = International Prognostic Scoring System; IPSS-R = revised IPSS; MDS = myelodysplastic syndromes; MI = myocardial infarction; NMSC = non-melanoma skin cancer; PD = progression of disease; VTE = venous thromboembolic event; WHO = World Health Organization,

^a As far as available in data sources and as per clinical practice

^b Cytogenetic risks will be categorized as described in the new cytogenetic scoring system (Schanz, 2012) that has been integrated into the IPSS-R (Greenberg, 2012).

Table 4: Therapy and Other Treatment Variables for Both On- and Off-label Cohorts

Variables ^a	
Lenalidomide Treatment	Indication of use, starting dose, dose adjustments, dose interruptions
Other MDS medications	Current use (yes, no); dose, response, duration of use
Prior ESA Treatment	Prior use (yes, no); prior response (yes/no), most recent treatment, duration of treatment
Other Prior MDS Treatments	Prior use (yes, no); prior response (yes/no), most recent treatment, duration of treatment
Concurrent ESA Use	Current use (yes, no); dose, response, duration of use
Concomitant Medications	Concomitant medications, duration of treatment
RBC transfusion	Yes/no, number of units over last 8 weeks (baseline and until PD)
Con = concomitant ESA	= erythropoiesis-stimulating agent. MDS = myelodysplastic syndromes

Con = concomitant; ESA = erythropoiesis-stimulating agent; MDS = myelodysplastic syndromes; Meds = medications; PD = progression of disease; RBC = red blood cell.

^a As far as available in data sources and as per clinical practice

Variables ^a	
Progression to AML ^b	Yes/no, date of event, and method of documentation
Death	Date and cause of death, and method of documentation
Adverse Events	Date of event (incidence) (using case definitions from NCI CTCAE where feasible) of hematologic and non-hematologic adverse events, including but not limited to neutropenia, thrombocytopenia, VTEs, infections, bleeding, and major cardiac events
SPM (Invasive [hematologic and solid tumors] and NMSC) ^c	Yes/no, date of event, and method of documentation

Table 5: Outcome Variables for Safety for Both On- and Off-label Cohorts

AML = acute myeloid leukemia; CTCAE = Common Terminology Criteria for Adverse Events; NCI = National Cancer Institute; NMSC = non-melanoma skin cancer; SPM = second primary malignancy; VTE = venous thromboembolic event.

- ^a As far as available in data sources and as per clinical practice
- ^b Vardiman, 2009.
- ^c Not including AML, which is considered disease progression in patients with myelodysplastic syndromes.

7.4 Data Sources

Celgene assessed the feasibility of this protocol using various potential data sources across the EU for the identification of off-label prescriptions and existence of longitudinal data to measure long-term outcomes of patients with MDS, including progression to AML. The sources of data for the primary drug-utilisation objective and the secondary safety objectives in this study will include, but will not be limited to:

- the existing academic EUMDS Registry
- the Spanish Registry of MDS or RE SMD (registro español de síndromes mielodisplásicos), coordinated by the Spanish Group of MDS [GESMD] who aims to promote and develop primary research on MDS, bringing together all those involved in research, diagnosis and management of patients with MDS.
- the Düsseldorf MDS Registry, who aims, as best possible, to biologically characterize MDS, anticipate the course of the disease, and find the most suitable therapies as a benefit for all MDS patients
- the online French Registry of MDS, coordinated by the French MDS group [GFM]), a non-profit organization that includes most French haematology centres, several of them registered as centres of excellence of the International MDS Foundation
- the Danish National Acute Leukemia Registry.

Additionally, the company-sponsored Connect[®] Myeloid Disease Registry (US Cohort Registry) will be used to address the secondary safety objectives (but not the primary drug-utilisation objective due to a different MDS indication approved in the US, which is for the treatment of patients with *transfusion-dependent anemia due to low- or intermediate-1-risk myelodysplastic syndromes [MDS] associated with a deletion 5q abnormality with or without additional*

cytogenetic abnormalities). The company-sponsored Connect[®] Myeloid Disease Registry is a non-interventional, prospective, longitudinal, observational, multicenter, US cohort registry study of patients with confirmed cases of newly diagnosed MDS, idiopathic cytopenia of undetermined significance, and AML.

A limitation of the selected EU data sources is that they collect data only from specific countries or patient catchment areas, hence they cannot provide complete representation of the actual real-world European drug-utilisation patterns. However, the EUMDS Registry captures high quality data from 17 EU countries, and it will be used to mitigate this limitation. Of these 17 countries in the selected data sources, results will be included from at least 10 EU countries that have lenalidomide reimbursement for the MDS indication. More EU countries will potentially be included, once they gain reimbursement for the MDS indication. In addition, the Spanish Registry of MDS, the Düsseldorf MDS Registry, the online French Registry of MDS, and the Danish National Acute Leukemia Registry will provide a comprehensive coverage of MDS patients in these four countries to complement the data in the EUMDS Registry. Adjustments will be made for any patients in the four national registries that overlap with patients in the EUMDS Registry.

Operational definition of variables will be consistent regardless of the data source.

To protect privacy and according to the local regulations, analysis of study endpoints will be conducted using aggregated data (majority of analyses) or performed by the local registries (Kaplan-Meier and multivariate analyses). To do the analyses which are based on aggregated data, datasets limited to the necessary variables will be compiled from pseudonymized datasets provided to the sponsor by each registry, and processed in accordance with the applicable regulations regarding privacy protection.

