7.1.2 Selection Criteria

7.1.2.1 Inclusion Criteria

- Patients with MDS commencing their treatment with lenalidomide after the granting of Regulatory approval for use in the treatment of MDS in the EU (EC Decision, 13-Jun-2013) and a subsequent positive reimbursement decision in the countries concerned, irrespective if the initial MDS diagnosis occurred before (prevalent patients) or after (incident patients) such date with the exception of eligible patients from the company-sponsored Connect[®] Myeloid Disease Registry (US Cohort Registry) who will be included regardless of start date of treatment
- Laboratory confirmation (morphological and cytogenetic) of MDS
- Patients with confirmed date of MDS diagnosis and lenalidomide treatment initiation
- Obtaining appropriate permission from the selected data sources to utilise the data

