7.1.2.2 Exclusion Criteria

- Patients receiving lenalidomide prior to regulatory approval for use in the treatment of MDS in the EU (EC Decision, 13-Jun-2013) in the countries concerned
- Patients treated with lenalidomide in an interventional therapeutic clinical trial for MDS

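### An MDS patient treated with lenalidomide but first registered at AML is eligible and a certain event, so AML incidence can be biased upward

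*Protocol*

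**What the plan says.** **Sources.** Section 7.4 lists "the Danish National Acute Leukemia Registry" among the sources for both the drug-utilisation and the safety objectives. Its entry criteria are not stated, but the same section says that the four national registries, this one included, "will provide a comprehensive coverage of MDS patients in these four countries to complement the data in the EUMDS Registry". Connect, used for the safety objectives only, covers "patients with confirmed cases of newly diagnosed MDS, idiopathic cytopenia of undetermined significance, and AML".

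**Eligibility.** Section 7.1.2.1 asks for "Patients with MDS commencing their treatment with lenalidomide after the granting of Regulatory approval for use in the treatment of MDS in the EU", for "Laboratory confirmation (morphological and cytogenetic) of MDS", and for "Patients with confirmed date of MDS diagnosis and lenalidomide treatment initiation". Connect patients are exempt from the start-date rule; they are those "who will be included regardless of start date of treatment". Section 7.1.2.2 has two exclusions: the first begins "Patients receiving lenalidomide prior to regulatory approval for use in the treatment of MDS in the EU", and the second concerns treatment within an interventional trial.

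**Time origin and analysis.** Section 7.1.1 starts the clock for AML, as for every other event, at the first lenalidomide dose. Section 7.7.3 plans a cumulative incidence of AML with a 95% CI in each cohort. It leaves Kaplan-Meier curves and Cox models to each registry on its own data.

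**Cohorts.** In section 7.2.1 the on-label cohort is confined to the EU, and the Connect exception appears only in the off-label definition.

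**The concern.** A registry that can take in a patient because AML has been diagnosed offers a route into the study that is open only to patients who progress. Take a patient with documented MDS who was treated with lenalidomide outside the registry and was first registered at AML. That patient meets every criterion and brings an event. A similar patient who did not progress has no matching way in through that route, so events are added without their share of event-free patients.

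The Study Size part of the Abstract makes AML in off-label patients the leading secondary aim, and this is the figure exposed. The study could overstate a safety signal that it was set up to describe. Section 7.9 discusses loss to follow-up, visit intervals, misclassification and missing data, but not entry brought about by the outcome.

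**Working it through.** **1. Follow one patient through the rules.** MDS is diagnosed and laboratory-confirmed, lenalidomide is started, AML is diagnosed, and only then is the patient registered.

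- MDS with laboratory confirmation (7.1.2.1): met.
- Confirmed dates of MDS diagnosis and lenalidomide start (7.1.2.1): met if the history was recorded.
- Start date: met if after EU approval in a reimbursing country; waived for Connect.
- Exclusions (7.1.2.2): neither mentions AML or the time of registration.
- AML outcome (7.1.1): counted from the first dose, so the event falls inside follow-up.

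The patient is eligible and is an event with certainty. Without the documented MDS, the first two checks fail and the patient stays out.

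**2. Reproduce the planned figure.** Section 7.5 assumes 230 off-label patients and 17% AML, with a 95% CI of 12.3% to 22.4%. The nearest count is 0.17 × 230 = 39.1, or 39 events. The exact (Clopper-Pearson) interval for 39/230 = 17.0% is 12.3% to 22.4%, which matches. Wald gives 12.1% to 21.8% and Wilson 12.7% to 22.3%; neither matches. The planned figure itself is not in dispute.

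**3. Illustrate the shift.** Let k be the number of patients registered only because AML had occurred, all of them events. The observed proportion becomes (39 + k)/(230 + k). The values of k are assumed; the protocol gives none.

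| k | Proportion | Exact 95% CI |
|---|---|---|
| 0 | 39/230 = 17.0% | 12.3% to 22.4% |
| 5 | 44/235 = 18.7% | 13.9% to 24.3% |
| 10 | 49/240 = 20.4% | 15.5% to 26.1% |
| 20 | 59/250 = 23.6% | 18.5% to 29.4% |

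The increase equals k(1 − p)/(N + k). With p = 39/230 and N = 230, k = 20 gives 20 × 0.830/250 = 6.6 percentage points. It shrinks as N grows. The 230 is half of the 460, a number that section 7.5 sets for patients treated after EU approval. Connect would also bring off-label patients registered at MDS, so the true N would be larger and the shift for a given k smaller than shown.

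**4. Which results are exposed.** Connect patients can appear only in the off-label cohort, so Connect has no on-label arm and yields no on/off hazard ratio of its own. Its effect is confined to the pooled off-label incidence and to any informal reading of that figure beside the on-label one. If entry at AML occurs in the Danish source, it could touch both cohorts, and the protocol does not fix the direction of its effect on a hazard ratio there.

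**5. Would exclusion alone suffice?** No. Suppose patients registered at or after AML are dropped but time still runs from the first dose. Everyone registered after the first dose is then AML-free by construction between dose and registration, which biases incidence downward. Risk time has to begin at registration for those patients.

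**The case against.** The strongest reply is that no affected patient is documented. Connect also enrols newly diagnosed MDS and undetermined cytopenia, and nothing shows that a treated MDS patient who transforms would be enrolled there as new AML. For the Danish source, entry through AML is inferred from the name alone, against the stated MDS coverage. A comment in Annex 2 says Danish exposure is taken from a dispensing registry and endpoints and covariates from national patient registries. It also names a Swedish database absent from section 7.4, so it may be out of date. It cuts both ways: such linkage could mean that entry does not depend on AML, or it could supply the earlier MDS and lenalidomide history of someone registered at AML.

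The MDS criteria are also a real safeguard. A reader might infer that AML patients without MDS can pass as MDS. They cannot: laboratory confirmation and both dates are required in every source, and the Connect exemption lifts only the start-date rule.

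Finally, delayed entry may be specified in the statistical analysis plan, which is not at hand. Section 7.7.3 also lists aggregated data by country where possible, and section 7.9 promises caution over differences between registries.

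What stands: these replies limit how likely and how large the bias is, but do not close the gap. The eligibility rules and the time origin are fixed in the protocol, and neither refers to registry entry. Tables 3 to 5 request neither the date of registration nor the diagnosis at registration. Without them, affected patients cannot be identified, because section 7.9 says raw data will not be pooled.

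**Conclusion.** The concern holds in a limited form. The protocol admits a lenalidomide-treated MDS patient whose registration was triggered by AML, counts that patient as an event from the first dose, and asks for no variable that would show it. Any such patients push AML incidence upward.

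The size is unknown. The range of 18.7% to 23.6% for 5 to 20 added patients rests on assumed counts and on a base of 230 that leaves out Connect's own patients who did not progress.

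Three stronger readings are not supported:

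- That both sources enrol because of leukaemia. AML is one of three Connect diagnoses, and the Danish entry rule is not stated.
- That Connect distorts the on/off hazard ratios. They are computed within each registry, and Connect has no on-label arm.
- That passing 22.4% crosses a threshold. That figure is a planned precision limit and triggers no decision.

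**What to change.** Leave section 7.1.2.1 and the primary use analysis as they are. An added eligibility line would remove patients from the drug-utilisation result, where the time of registration does no harm of this kind.

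In section 7.7.3, for the AML analyses only:

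- Collect the date of registry entry and the diagnosis at entry, and add both to the variable tables in section 7.3.
- Exclude patients whose AML was diagnosed at or before registry entry, and report how many there were, by source and cohort.
- Keep the first dose as time zero, but let patients registered after it join the risk set at registration (left truncation). Both comparative studies described in section 5.2 used this method to deal with differing starts of follow-up. It needs individual dates, so it should go into the instructions that section 7.6 already has the sponsor send to the registries.
- Report AML incidence with and without the Danish and Connect sources.

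State the Danish registry's entry criteria in section 7.4. If it does register MDS patients comprehensively, the exclusion will remove few or none there.

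Cost: one or two extra variables from each registry, one sensitivity analysis, and the loss of a few patients and events from the AML analysis.

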7.5 Study Size

The study population will be composed of at least 460 patients with MDS treated with lenalidomide after the granting of Regulatory approval of Revlimid (lenalidomide) for use in the treatment of MDS in the EU (EC Decision, 13-Jun-2013) in the countries concerned. The final data analysis will include all patients eligible for this study at the end of data collection.

An interim descriptive report was prepared 1 year after study start. Within the interim descriptive report, available data on eligible patients regarding the pattern of use of lenalidomide within and outside the EU approved indication, namely the distribution of MDS patients according to predefined categories (eg, transfusion-dependent IPSS low- or int-1-risk MDS with isolated del(5q), or with additional cytogenetic abnormalities, or IPSS risk categories int-2 or high, or patients with MDS without del(5q)) was presented. On 29-Mar-2019, the first interim descriptive report was submitted to the Pharmacovigilance Risk Assessment Committee (PRAC) in order to discuss if the data collected on lenalidomide use, across different groups of MDS patients, are sufficient to allow successful completion of this study. The Assessment Report adopted by the CHMP on 27-Jun-2019 included a request to submit another interim descriptive report in Quarter (Q)1 2020. On 27-Mar-2020, the second interim descriptive report was submitted to PRAC (EMEA/H/C/000717/ANX/041.8). The final Assessment Report, adopted by the CHMP on

10-Dec-2020, concluded that the post-authorisation measure for the second interim report was fulfilled with no further action required.

The data on patients treated with lenalidomide for MDS will only be available within a country following EU-approval of the product for the MDS indication and once available in the selected data source. Therefore, this study will be limited to countries that gave a subsequent decision to fully reimburse lenalidomide for the MDS indication and the extent of data per country will be related to time since the EU-approval for the MDS indication and availability of data with the exception of eligible patients from the company-sponsored Connect[®] Myeloid Disease Registry (US Cohort Registry) who will be included regardless of start date of treatment (see Section 7.4 [Data Sources]).

This retrospective drug-utilisation study will include patients with MDS treated with lenalidomide, irrespective if within or outside the approved indication in the EU (eg, patients commencing lenalidomide treatment for transfusion-dependent IPSS low- or int-1-risk MDS with isolated del(5q), or with additional cytogenetic abnormalities, or IPSS risk categories int-2 or high, or patients with MDS without del(5q) will also be recorded).

The primary objective of the study is to evaluate the proportion of patients outside of the EU approved indication (off-label). Feasibility assessments indicated that off-label use of lenalidomide in MDS in the EU is infrequent (5% to 22% with a large margin of error at either end). However, the second interim descriptive report submitted to PRAC on 27-Mar-2020 (EMEA/H/C/000717/ANX/041.8) showed a higher level of off-label use. The proportion of MDS patients treated in an off-label setting was high, with 57.0% of MDS patients treated off-label (n = 212) versus 40.1% of MDS patients treated on-label (n = 149), and 2.9% of patients with an unknown label status (n = 11). Assuming that the final percentage of off-label patients will be around 50%, a sample size of 460 patients will yield a 95% CI = (45.4%, 54.6). The sample size calculated would not only allow to investigate this assumption, but also will detect smaller percentages if the true proportion would be smaller.

Assuming a proportion of around 50%, around 230 patients in the study will be off-label. Assuming the proportion of patients progressing to AML will be similar to those on-label, ie, 17%, 230 off-label patients will yield a 95% CI = (12.3%, 22.4%).

7.6 Data Management

Study Monitoring and Source Data Verification

The data is in this study will be owned by the data owners including, but not limited to, the data sources described in Section 7.4. All individual data management, data security, and data protection requirements will be the responsibility of the data owners (ie, registries). For all results provided to Celgene, security of the results will be maintained at all times in line with applicable local law and procedures. Access to results will be limited to authorised individuals. Controls, such as document encryption, will be used to ensure the authenticity, integrity, and confidentiality of electronic records when transmitted over open systems (eg, the internet). Adequate back up of the data will be maintained throughout the course of the study.

The management of missing data as potential sources of study biases will be done when analyzing the distribution of available data on eligible patients and the outcomes from longitudinal follow-up, as described in Section 7.9 "Limitations of the Research Method".

The data required for classifying patients as on- or off-label are critical to satisfy the primary objective of this study. An attempt will be made to obtain values when data are missing. However, if data cannot be found to classify lenalidomide patient as on- or off-label, that patient cannot be classified and will be dropped from the primary analysis.

For the analyses of time to progression to AML (Kaplan-Meier and multivariate analyses adjusted for confounding and risk factors) to be performed at the end of study, data owners will be provided with instructions and will be requested to perform this analysis on an individual registry basis. This approach will ensure that all data have appropriate legal and data protection requirements fulfilled. All such data will be pseudonymized by the registries and processed in accordance with local regulations regarding privacy protection.

